6.3 Safety Analysis Set

The Safety Analysis Set comprises all subjects in the ATS Analysis Set who receive at least 1 dose of investigational product (IP) and will be analyzed using the actual treatment received. The actual treatment is planned to be CSL312 for all subjects.

Technical Note: The handling of unplanned dosing deviations for individual subjects will be discussed and decided at the Planned Analyses Review Meeting (PARM). Unless stated otherwise below, the treatment will be considered the same whether administered with NSD or AI.

The loading dose for CSL312-naïve subjects will be shown as part of the 200 mg dose.

6.4 Per Protocol Analysis Set

The Per-protocol (PP) Analysis Set comprises all subjects in the ATS Analysis Set who receive at least 1 dose of IP and who comply with the protocol. Decisions regarding exclusion from the PP Analysis Set will be made and documented before DBL.

Technical Note: unless stated otherwise below, the treatment will be considered the same whether administered with NSD or AI.

6.5 Pharmacokinetic Analysis Set

The PK Analysis Set comprises all subjects in the Safety Analysis Set who receive an injection of CSL312 with at least 1 measurable concentration of CSL312.

6.6 Pharmacodynamic Analysis Set

The PD Analysis Set comprises all subjects in the Safety Analysis Set for whom at least 1 PD measurement was obtained.

7 General Considerations

Datasets will be created according to Clinical Data Interchange Standards Consortium (CDISC) standards. Study data will be provided in Study Data Tabulation Model (SDTM) format. Analysis data will be provided in Analysis Data Model (ADaM) format.

SAS version 9.4 or higher will be used to perform all data analyses.

Summaries of continuous variables will be in terms of the number of observations, mean, standard deviation (SD), median, first quartile (Q1), third quartile (Q3), 95% confidence interval (CI), minimum, and maximum. Other descriptive statistics (eg, standard error, coefficient of variation) may be reported when appropriate. Categorical variables will be summarized using frequency counts and percentages. Analyses that use other descriptive statistics will have the specific descriptive statistics identified with the analysis in the applicable SAP section.

All listings will contain the subject identifier (ID). Listings will generally be sorted first by site and within site by subject ID.

The main listing of TEAEs (see [Section 11.4](#)) and the listing of individual HAE attacks (see [Section 10.2.1](#)) will include the most recent CSL312 dose (level, device [NSD or AI] and date).

7.1 Treatment Descriptors

For efficacy, PK and PD analyses (see [Section 10](#)) all subjects regardless of used administration device (NSD or AI) will be displayed under the 200mg CSL312 dose. Per the original protocol it was planned that for safety, PK and PD analyses (see [Sections 11, 12](#) and [13](#) respectively) subjects would be displayed under their actual dose, which could have been 200 mg, 400 mg or 600 mg CSL312.

Per Amendment 1 subjects will still be shown under their actual dose, but dosing modifications will not be permitted, and all subjects receive 200 mg CSL312. As no dosing modifications occurred before Protocol Amendment 1, all subjects will be shown under the actual dose level of 200 mg CSL312. Columns for 400 mg and 600 mg CSL312 will not be required. If there should be unplanned dosing different from the planned 200 mg CSL312, it will be discussed and documented during the PARM how this will be handled in the analysis.

For AE tables, treatment may be further differentiated by administration device in use when the AE started:

- 200mg CSL312 AI,
- 200mg CSL312 NSD,
- 200mg CSL312 Overall.

8 Data Handling Conventions

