- M: Subjects may use the on-demand medication of their choice to treat HAE attacks experienced during the study if that medication has previously been shown to be effective.
- N: For CSL312 naïve subjects, the first dose of CSL312 will be a loading dose consisting of 2 SC injections of 200 mg CSL312 each for a total of 400 mg CSL312. Subjects rolling over from the CSL312_3001 study will not receive a loading dose. Subjects will be trained in CSL312 self-administration at Baseline, Months 1, 2 and 3 visits. Starting at Month 4, all subjects will self-administer at home monthly.
- O: Subjects will complete the Medication Dosing Diary on the eDiary at site visits (ie, Day 1, Months 1, 2, and 3) and then monthly at home through the End of Treatment Visit.

Schedule of Assessments: Treatment Period (CSL312_2001 Subjects)

Study Period		Treatment Period						End of Treatment ^A	Final Visit ^B /Follow-up (2 months after End of Treatment Visit)
Month		3	6	12	18	24	30		
Visit Day		1	91	181	361	541	721	901	
Visit Window (Days)			±4d ^C	±4d ^C	±4 ^C	±4d ^C	±4d ^C	±4d ^C	±7d
Study center visit		X	X	X	X	X	X	X	
Written informed consent		X							
Confirm eligibility for Treatment Period ^D		X							
Physical examination ^E		X	X	X	X	X	X	X	
Vital signs, body weight, and height ^F		X	X	X	X	X	X	X	
SGART and IGART					X		X		
TSQM II (subjects ≥ 18 yrs), AE-QoL (subjects ≥ 18 yrs), WPAI:GH (subjects ≥ 16 yrs) ^G		X		X	X	X	X		
Urine collection for urinalysis (central lab)		X		X	X	X	X	X	
Blood Draws^I (central lab)	Hematology / Biochemistry / Coagulation	X		X	X	X	X	X	
	Retention sample for HAE biomarkers ^H	X	X	X	X	X	X	X	
	Pharmacokinetics / Pharmacodynamics	X	X	X	X	X	X	X	
	Immunogenicity	X		X	X		X		
Pregnancy test ^J		X	X	X	X	X	X	X	
PRO / eCOA tablet training		X							
Review of eDiary instructions with subject		X							
Review eDiary data and assess / document HAE attacks			X	X	X	X	X	X	X
eDiary deactivation ^K									X
Confirm access to on-demand HAE medication ^L		X	X	X	X	X	X	X	
IRT CSL312 kit assignment		X	X	X	X	X	X	X	
Accountability of CSL312		X	X	X	X	X	X	X	
Administration of CSL312 at site ^{M,N}		X							
Concomitant medications and therapies									
Adverse events									

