Abbreviations: AI = autoinjector; HAE = hereditary angioedema; IGART = Investigator's Global Assessment of Response to Therapy; IRT = interactive response technology; NSD = needle safety device; PRO = patient reported outcome; QoL = Quality of Life; SGART = Subject's Global Assessment of Response to Therapy; TSQM II = Treatment Satisfaction for Medication Questionnaire version II; WPAI:GH = Work Productivity and Activity Impairment: General Health; yrs = years.

Footnotes to the Schedule of Assessments: Treatment Period for All Subjects Under Amendment 1

- A: End of Treatment can replace any of the planned site visits (eg Visit Month 36) and should occur 1 month after last dose of CSL312 but no later than September 2025. The End of Treatment Visit may vary per individual subject depending on the end of study in their respective country as per [Section 3.4](#). Any visit beyond Month 36 requires approval from the Sponsor.
- B: Follow-up Visit will be conducted via telephone call only.
- C: Treatment Period visits have \pm 4 day window, with a maximum of 34 days between any 2 doses.
- D: The specific site visit to consent into Amendment 1 and to switch to CSL312 200 mg AI may vary per individual subject. Consent into Amendment 1 and switching to CSL312 200 mg AI may occur starting at the Month 12 Visit. An unscheduled visit to accommodate consent into Amendment 1 and switching to CSL312 200 mg AI (with no other assessments performed at this visit) may be scheduled as needed at dates planned for home doses; this unscheduled visit should be performed according to the dosing schedule. The first administration with CSL312 200 mg AI will always occur at the site. Subjects who decline switching to CSL312 200 mg AI and who have participated in the study for at least 12 months will receive 1 more dose of CSL312 200 mg NSD at the time of the scheduled site visit and subsequently proceed with the End of Treatment Visit 1 month later, as well as a Follow-up Visit 2 months after the End of Treatment Visit, as per the original protocol.
- E: A physical examination will be conducted per the investigator's standard procedure and will also include assessment of unilateral pain and / or swelling of the lower extremities for the purpose of screening for deep vein thrombosis.
- F: Investigator completes IGART in Rave. Subjects complete SGART in tablet.

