9.4 Observation Period for Adverse Events

The observation period for the reporting of AEs (and SAEs) for an individual subject will start at the time of giving written informed consent for participation in the current study and finish upon the subject's final visit.

If the investigator becomes aware of an SAE that has started after the observation period has finished, and there is at least a possible causal relationship with the investigational product or medical device constituent, the event must be reported to the Sponsor following the same timelines and procedures described for SAEs occurring during the study (see [Section 9.6.3](#)).

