9.6 Adverse Event Reporting

9.6.1 Adverse Events

At each clinical evaluation, the investigator (or delegate) will determine whether any AEs have occurred. All AEs are to be recorded in the CRF. If known, the medical diagnosis of an AE should be recorded in preference to the listing of individual signs, laboratory findings, and / or symptoms. The investigator must follow up on the course of an AE until resolution or stabilization. If an AE is ongoing after the end of study visit, the AE will continue to be followed up until resolution, stabilization, or the subject is lost to follow-up.

If, during the study period, a subject presents with a preexisting condition that was not noted at the time of study entry, the condition should be retrospectively recorded in the Medical History CRF.

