10.3.2 Analyses of the Primary Endpoint

The TEAEs for all C1-INH HAE subjects receiving CSL312 once monthly, independent of the use of CSL312 200 mg AI or CSL312 200 mg NSD, will be summarized using the Safety Analysis Set. TEAEs are AEs that start on or after the date and time of the first administration of study treatment. TEAEs occurring until the Follow-up Visit will be summarized. TEAEs with completely or partially missing date or time will be considered treatment-emergent following the worst-case principle, unless the partial date clearly indicates that the AE started before the first administration of study treatment.

TEAEs will be summarized by the number of subjects and percentage of subjects experiencing at least 1 TEAE, the number of events, as well as the event rates per injection and per subject year. TEAEs will be presented for the following:

- All subjects in the Safety Analysis Set (ie, subjects on 200 mg CSL312 once monthly)
- Subjects on 200 mg CSL312 monthly and using CSL312 200 mg AI
- Subjects on 200 mg CSL312 monthly and using CSL312 200 mg NSD

TEAE rates per injection will be calculated as follows:

$$\text{TEAE Rate per Injection} = \frac{\text{Number of TEAE}}{\text{Number of injections}}$$

where number of injections will be the sum of the injections that subjects received during the respective safety evaluation period.

TEAE rates per subject years will be calculated as follows:

$$\text{TEAE Rate per Subject Year} = \frac{\text{Number of TEAE}}{\text{Subject years}}$$

where subject years will be the sum of the time in years that subjects were exposed to study treatment during the respective safety evaluation period.

An overview summary of TEAEs will be provided including:

- TEAE
- SAEs
- Deaths
- TEAEs occurring within 24 hours of investigational product administration
- Related TEAEs
- TEAEs leading to study discontinuation
- TEAEs in each severity category
- TEAEs in each outcome category
- AESIs

A summary table by SOC and PT and an overview summary table of COVID-19 associated TEAEs and a listing showing all COVID-19 associated AEs will be provided.

TEAEs which can be clearly identified to be related to an HAE therapy medication other than CSL312 during the Follow-up Period will be flagged in listings and will be summarized separately.

The overview summary and the summary table by SOC and PT will also be provided for TEAEs occurring while using CSL312 200 mg AI and occurring while using CSL312 200 mg NSD.

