11.3 Analysis of Primary Safety Endpoint

All analyses described in this section are applicable for C1-INH HAE subjects only. TEAEs will be presented for the following:

- All subjects in the Safety Analysis Set (all subjects on 200 mg CSL312 once monthly, independent of the use of CSL312 200 mg AI or CSL312 200 mg NSD).
- Subjects on 200 mg CSL312 using AI.
- Subjects on 200 mg CSL312 using NSD.

TEAEs will be summarized by the number of subjects and percentage of subjects experiencing at least 1 TEAE, the number of events, as well as the event rates per injection and per subject year.

TEAE rates per injection will be calculated as follows:

$$\text{TEAE Rate per Injection} = \frac{\text{Number of TEAEs}}{\text{Number of injections}}$$

where the number of injections will be the sum of the injections that subjects received during the respective safety evaluation period with the respective device (NSD, AI, or overall) the TEAE is assigned to.

TEAE rates per subject years will be calculated as follows:

$$\text{TEAE Rate per Subject Year} = \frac{\text{Number of TEAEs}}{\text{Subject years}}$$

where subject years will be the sum of the time in years that subjects were exposed to study treatment using that device (NSD, AI, or overall) during the respective safety evaluation period.

An overview summary of TEAEs will be provided including:

- TEAE,
- SAEs,
- Deaths,
- ISRs,
- TEAEs occurring within 24 hours of start of IP administration,
- SAEs occurring within 24 hours of start of IP administration,
- Related TEAEs,
- Related SAEs,
- TEAEs leading to study discontinuation,
- TEAEs in each severity category,
- ISRs, in each severity category,
- TEAEs in each outcome category,
- SAEs in each severity category,
- SAEs in each outcome category,
- AESIs, both as reported by the investigators and as identified via SMQ (see [Section 11.4](#) for definitions).

A summary table by SOC and PT will be provided.

These two summaries will exclude all TEAEs clearly identified to be related to an HAE therapy other than CSL312 during the Follow-up Period. Both summaries will be repeated for TEAEs that can clearly be identified to be related to an HAE therapy medication other than CSL312.

To evaluate the COVID-19 impact on the primary endpoint the overview summary of TEAEs and the summary table by SOC and PT will be repeated as a sensitivity analysis excluding all COVID-19 related TEAEs (per the corresponding SMQ).

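### The autoinjector (AI) and needle safety device (NSD) adverse event columns in SAP 11.3 and 11.4 cover different parts of the study and are not comparable; the direction of the net bias is unknown.

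*SAP*

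**What the plan says.** **Columns.** SAP 7.1: "For AE tables, treatment may be further differentiated by administration device in use when the AE started". SAP 11.3, the primary safety analysis, lists all subjects, then "Subjects on 200 mg CSL312 using AI" and "Subjects on 200 mg CSL312 using NSD". SAP 11.4 repeats the three groups for the secondary tables. Protocol 10.3.2 likewise asks for summaries of "TEAEs occurring while using CSL312 200 mg AI and occurring while using CSL312 200 mg NSD". Each column carries counts, percentages, and rates per injection and per subject-year.

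**Start of AI.** Protocol, Amendment 1 Schedule of Assessments (footnote D) and 8.6.6.1: "Consent into Amendment 1 and switching to CSL312 200 mg AI may occur starting at the Month 12 Visit".

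**AE elicitation.** Protocol 9.6.1: "At each clinical evaluation, the investigator (or delegate) will determine whether any AEs have occurred". CSL312-naïve and CSL312_3001 subjects have visits at Months 1, 2, 3, 6, 9 and 12, then every 6 months. CSL312_2001 subjects have visits at Months 3, 6 and 12, then every 6 months. Amendment 1 visits are every 6 months from Month 12.

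**Early NSD time.** Naïve subjects receive the loading dose on Day 1. For naïve and CSL312_3001 subjects, footnote N of their schedule adds: "Subjects will be trained in CSL312 self-administration at Baseline, Months 1, 2 and 3 visits".

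**Allocation rules.** In SAP Table 3 a switcher's NSD safety period ends the day before the first AI dose, and the AI safety period runs to the Follow-up Visit. SAP 11.2 places a switcher's TEAE with a missing start date on AI unless other date information shows that it began earlier. SAP 11.4 plans TEAEs by 3-month window but keeps the cumulative safety period as the basis for the rates.

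**The concern.** Device is tied to time on study. NSD alone carries the first year: the loading dose, first exposure for treatment-naïve subjects, supervised early dosing and, for naïve and CSL312_3001 subjects, AE questioning every 1 to 3 months. AI carries later time, in people who remained at least 12 months and accepted the change. Device-specific denominators adjust for the length of time on each device, not for whether that time is early or late.

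Laboratory detection differs too. Under Amendment 1, blood safety tests become yearly and urinalysis stops at the consent visit.

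Protocol 3.3.1 says the autoinjector is meant for later commercial use, and the only other AI study the protocol names is a pharmacokinetic comparison in healthy subjects (1.2.3.1). Readers will therefore look to these columns for the device's safety in patients, and a gap in either direction could be credited to the device when it comes from the calendar.

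**Working it through.** The documents give no figure for an AI–NSD comparison. Their one design figure, in Protocol 10.1, reproduces: 1 − 0.97^100 = 0.952 against the stated 95%. It does not bear on this point.

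**Step 1. Scheduled visit gaps, from the visit days**

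| Period | Gaps (days) | Mean |
|---|---|---|
| NSD to Month 12, naïve/3001 | 30, 30, 30, 90, 90, 90 | 60 |
| NSD to Month 12, 2001 | 90, 90, 180 | 120 |
| NSD after Month 12, all | 180 each | 180 |
| AI | 180 each | 180 |

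The difference in interval lies wholly in the first NSD year.

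**Step 2. Recall alone, at equal true event rates.** Assumption: the chance that an event is still reported decays at k per month since onset. Over an interval of T months the mean chance is f(T) = (1 − e^(−kT))/(kT). At k = 0.10, f(1) = 0.9516, f(2) = 0.9063, f(3) = 0.8639 and f(6) = 0.7520.

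For a naïve/3001 subject:
- NSD, first year: (3 × 0.9516 + 9 × 0.8639)/12 = 0.8859
- All NSD, switch at Month 18: (12 × 0.8859 + 6 × 0.7520)/18 = 0.8412
- All NSD, switch at Month 24: (12 × 0.8859 + 12 × 0.7520)/24 = 0.8189
- AI: 0.7520

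AI/NSD is 0.894 (switch at Month 18) or 0.918 (Month 24), so AI is 11% or 8% low. Across k = 0.05 to 0.20 the ratio runs from 0.944 to 0.808 (Month 18) and from 0.958 to 0.848 (Month 24). For a CSL312_2001 subject switching at Month 24 with k = 0.10, all NSD is (6 × 0.8639 + 18 × 0.7520)/24 = 0.7800 and the ratio is 0.964.

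**Step 3. Add the follow-up that the SAP places in the AI period.** Assumptions: 12 months and 12 injections on AI, then 2 months without injections, the same true event rate, and a 2-month recall interval. Relative to the true monthly rate, AI events = 12 × 0.7520 + 2 × 0.9063 = 10.84.

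| AI measure (k = 0.10) | Value | AI/NSD, switch at Month 18 | AI/NSD, switch at Month 24 |
|---|---|---|---|
| Per injection: 10.84/12 | 0.903 | 1.07 | 1.10 |
| Per unit time, follow-up in denominator: 10.84/14 | 0.774 | 0.92 | 0.95 |

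If follow-up is left out of the subject-year denominator, the per-injection ratios apply there as well. SAP 11.1 and 11.3 do not say where exposure time ends.

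**Step 4. How far the sign depends on unknowns.** Let s be relative ascertainment on AI and T the months on AI, with follow-up events counted at the same rate. The per-injection ratio is s(T + 2)/T, so AI looks lower only if s is below T/(T + 2): 0.75, 0.86, 0.90, 0.92 or 0.94 for T = 6, 12, 18, 24 or 30. At s = 0.9 the ratio is 1.20, 1.05, 1.00, 0.98 or 0.96.

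**The case against.** A reader might infer that the autoinjector will look safer than it is. Longer recall, fewer laboratory tests, survivor selection and a loading dose counted as one injection on NSD (SAP 8.2.6) all push that way. The documents do not support the inference, because follow-up after EOT and the default for undated events push a switcher's AI column up. A first-year comparison, which gives 0.7520/0.8859 = 0.849 or 15% low at k = 0.10, is not the planned one either: the SAP column is all NSD time, part of it on the same 6-monthly visits.

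Other points for the plan also have force:
- The AE window is continuous on both devices: "The observation period for the reporting of AEs (and SAEs) for an individual subject will start at the time of giving written informed consent".
- Between visits, HAE-type symptoms entered in the eDiary alert the site on either device, and symptoms not confirmed as an attack become AEs.
- Home dosing is not specific to AI. NSD is given at home from Month 4, or after the first dose for CSL312_2001 subjects.
- The loading dose concerns naïve subjects only, and first exposure concerns treatment-naïve subjects only.
- No device contrast or hypothesis test is planned, and the main analysis pools the devices.
- TEAE counts by 3-month window and device are already planned.

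These limit the claim without removing it. The alert covers HAE-type symptoms, not AEs in general. The window tables give counts, but their rates are not based on time within the window. Descriptive columns placed side by side will still be compared, and the SAP gives no warning against it.

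**Conclusion.** The point stands as one of non-comparability. In SAP 11.3 and 11.4 device is confounded with time on study, first-year visit density, laboratory frequency and selection, and the period definitions give AI all of a switcher's follow-up.

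The net direction is unknown and can differ between the two planned rates. At k = 0.10 and identical device safety, recall alone puts AI 8 to 11% below all NSD for a naïve/3001 subject. With 12 months on AI and follow-up counted, AI is 7 to 10% above per injection, yet 5 to 8% below per subject-year if follow-up is in the denominator. Decay rate, switch month, time on AI and the follow-up event rate are assumptions; the documents supply none of them. The sizes are illustrative, and the effects of early reactions, selection and undated events are not quantified. The pooled primary summary is not affected by the device split.

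**What to change.** In SAP 11.3 and 11.4:
1. Split the NSD column at the Month 12 Visit (Day 361). Set AI against NSD time from Month 12, and show Month 0–12 NSD separately. This equalises the scheduled visit gap at 180 days and takes the loading dose and first-year exposure out of the comparison.
2. Show events before and after EOT separately, and define exposure time by device to match.
3. For the 3-month-window TEAE tables by device, base rates on exposure within the window.
4. Footnote that the all-NSD column is not comparable with AI, and that laboratory frequency and the selection of switchers still differ after the split. Under the original protocol, blood tests and urinalysis continue at Months 12, 18, 24 and 30.

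All of this uses dates already collected, at the cost of one column, a few denominators and a footnote. The downside is less NSD exposure in the closer comparison. A subject who switches at Month 12 contributes none, and one who declines the switch after 12 months receives only one more NSD dose before EOT. Changing data collection is no longer practical: Amendment 1 puts EOT no later than September 2025, and SAP version 2.0 is dated 02 Oct 2025.
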